10.2. Concomitant and Other Medications

Concomitant medication information will not be summarized in this study.

10.3. Routine Laboratory Data

Not done for this study.

10.4. Vital Signs

Vital signs (blood pressure, pulse, respiratory rate, and body temperature) will not be summarized in this study. The safety profile of florbetapir F 18 is well-characterized and no safety issues related to vital signs are expected. Should safety analyses from this study indicate that vital sign data should be examined more carefully, post hoc tables and listing will be generated.

10.5. Study Termination Status

For this protocol, the end of study is defined as the completion of 24-48 hours follow up phone call post ¹⁸F-florbetapir scan. The reason for study termination will also be summarized in disposition table. The primary reasons for study termination include: completed study, lost to

follow-up, consent withdrawn, administrative decision, and others.

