Each study participant will be contacted by phone 24-72 hours after they were injected with the investigational agent to confirm their well-being and query them about any new adverse events that may have occurred within 24 hours post-injection.

Repeat imaging:

Longitudinal imaging studies may be conducted under protocol ¹⁸F-AV-45-A14, with prior sponsor approval and at the discretion of the investigator. In these studies subjects may have up to two imaging sessions within a 12 month timeframe. Procedures for each day will be identical to those described above.

Evaluation of Imaging:

Images will be evaluated qualitatively and/or quantitatively:

- Images will be visually examined by a trained radiologist or nuclear medicine physician
 who is blinded to the subject diagnosis and will be reported as either Aβ positive or Aβ
 negative.
- SUV for target areas such as frontal cortex, temporal cortex, parietal cortex, posterior cingulate cortex, anterior cingulate and precuneus, and reference regions including cerebellum will be calculated. SUVR for cortical target areas relative to cerebellum will also be calculated.

Statistical Methods:

General Statistical Considerations

All values will be summarized by diagnostic groups. Generally, patients should be classified as Alzheimer's disease (AD), mild cognitive impairment (MCI) or cognitively healthy volunteers in accordance with the classification guidelines in Appendix 11.3. However, alternative criteria may be used if specified in the companion protocol. Frequency distributions including counts and percents will be included for all categorical outcomes. Summary statistics including mean, standard deviation, median, minimum and maximum values will be presented for all continuous outcomes.

Populations for Analysis

IND Sponsor:	Name of Compound:	
Avid Radiopharmaceuticals, Inc.	Injection	(E)-4-(2-(6-(2-(2-(2-[¹⁸ F]fluoroethoxy)ethox y)ethoxy)pyridin-3-yl)vinyl)-N- methylbenzenamine

The efficacy population will include all patients for whom image data are available. All analyses involving amyloid imaging outcomes will be based on the efficacy population. All subjects who receive florbetapir will be included in the safety population.

Efficacy (Imaging Results)

- Qualitative assessment of image (A β + or A β -)
- Quantitative assessment (SUVR) associated with the following brain regions:

Frontal cortex

Temporal cortex

Parietal cortex

Posterior cingular cortex

Anterior cingulate

Precuneus

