5. INVESTIGATIONAL PLAN

5.1 Overall Design and Plan of Trial

Protocol ¹⁸F-AV-45-A14 is designed to expand the database of florbetapir F 18 safety and amyloid binding as measured by PET imaging, and to provide standardized conditions for florbetapir F 18 use, data collection and analysis to facilitate companion studies including, but not limited to, longitudinal studies of aging, studies of progressive cognitive impairment and studies of imaging and blood/CSF biomarkers of neurodegenerative disease. Approximately 1,800 subjects will be studied under this protocol.

Screening assessments may take place over several days and will include collection of demographic information, a medical assessment for eligibility, and a brief cognitive interview, including an MMSE. Investigators will be encouraged, but not required, as part of their companion studies, to collect certain common data, such as Uniform Data Set cognitive assessments and MRI scans according to the Alzheimer's Disease Neuroimaging Initiative protocol, to facilitate potential pooling of data by and among investigators.

Subjects who qualify for the study will come to the imaging center at a later date and will have catheter(s) placed for i.v. administration of Florbetapir F 18 Injection. Vital signs will be taken in a supine position immediately prior to administration of florbetapir F 18 (within 30 minutes prior to injection). Subjects will receive a single i.v. bolus of florbetapir F 18, followed by brain PET imaging of 10 minutes duration, approximately 50 minutes post-dose injection. Sites with dynamic PET acquisition capabilities may elect to acquire a 20 minute acquisition, beginning 30 to 50 minutes post injection. If a 20 minute acquisition is chosen, the site will reconstruct at least one 10 minute image from the dataset in addition to a 20 minute reconstruction. All datasets will be submitted to the sponsor for analysis. Sites may elect additional imaging timepoints with prior approval from sponsor.

Adverse events will be continuously monitored during the imaging session. Subjects who experience any adverse event will not be discharged until the event has resolved or stabilized. A follow-up phone call to the patient (or the caregiver as applicable) will be conducted 24-72 hours after the imaging session to confirm patient well-being and to collect information about any new adverse events that may have occurred within 24 hours post-injection.

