- With prior sponsor approval and at the discretion of the investigator, a subgroup of not more than 5 subjects will be given the option of having a regimen of arterial blood sampling with up to 70 minutes of imaging beginning immediately after florbetapir F 18 administration. See Appendix 11.4 for detailed instructions on arterial blood sampling;
- Subjects will be observed continuously for signs of adverse events or serious adverse events;
- The injection site will be observed for excessive inflammation or damage to the surrounding tissue where the dose was injected; and
- A physician or physician designee will see the patient prior to dosing and prior to discharge.

Follow-Up:

Each study participant will be contacted by phone 24–72 hours after they were injected with the investigational agent to confirm their well-being and query them about any new adverse events that may have occurred within 24 hours post-injection.

Repeat Imaging:

Longitudinal imaging studies may be conducted under protocol ¹⁸F-AV-45-A14, with prior sponsor approval and at the discretion of the investigator. In these studies subjects may have up to two imaging sessions within a 12 month timeframe. Procedures for each day will be identical to those described above.

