4. STUDY DURATION AND VISIT SCHEDULE

The following flow chart describes the study duration and visit schedule:

Evaluations	Screen	Pre-dose	Dose	Injection Circulation (0 – 50 minutes) ³	Continuous PET Imaging 10 minutes	End of Imaging	24-72 hours post injection
Signed Consent	X						
Medical / Disease History	X						
Concomitant Meds	X	X					
MMSE	X						
Physician Visit	X	X ¹				X ¹	
Vital Signs		X					
Urine Pregnancy Test	X	X					
Florbetapir F 18 Administration			X				
PET Imaging ²					Continuous 10 minute scan - 50 minutes after dose injection		
Follow-up Phone Call							X
Adverse Event Assessment	X	X	X	X	X	X	X ³

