5.3. Follow up

A follow-up phone call to the subject (or the caregiver as appropriate) will be conducted approximately 24-48 hours after the imaging session to confirm their well-being and query them about any new adverse events.

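### SAP 10.5 ties end of study to a 24-48 hour call, while the protocol and the SAP's own flow chart allow 24-72 hours, so read literally a compliant subject called at 48-72 hours does not reach end of study

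*SAP*

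**What the plan says.** The follow-up call is the last contact after each imaging session, and the two documents time it differently.

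- **SAP 10.5:** "the end of study is defined as the completion of 24-48 hours follow up phone call post" the scan. The section then says the reason for termination goes into the disposition table and lists categories: "The primary reasons for study termination include: completed study, lost to" follow-up, withdrawal of consent, an administrative decision and a residual category.
- **SAP 5.3:** the call is "conducted approximately 24-48 hours after the imaging session to confirm their well-being".
- **SAP 4 (flow chart):** the call column is headed "24-72 hours post injection".
- **Protocol synopsis, Follow-up:** "Each study participant will be contacted by phone 24-72 hours after they were injected with the investigational agent".
- **Protocol 5.1:** the call is "conducted 24-72 hours after the imaging session to confirm patient well-being".
- **Protocol 7.1:** "Each study participant will be contacted by phone 24–72 hours after they were injected with the investigational agent".
- **Protocol 11.2 (flow chart):** the same column heading as the SAP flow chart.

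SAP 2 says the SAP is to be read together with the protocol, and no text in the SAP declares or explains a shorter call window.

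**The concern.** The end-of-study sentence in SAP 10.5 is the only text in the SAP that could define completion, and it stands directly before the completed-study category. It uses a narrower window than the schedule that sites were told to follow. A subject called in the third day after injection did what the protocol asked but falls outside the rule as written.

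The SAP has dropped the efficacy, vital-sign and concomitant-medication summaries. What remains is mainly adverse events, demographics and disposition, and the disposition table is where a reader would look to see how many injected subjects were followed to the end. One programmer might count any completed call and another might apply 24-48 hours as written. They could produce different completion counts from the same data, and the text does not settle which is intended.

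**Working it through.** No sample size, power or alpha figure is involved. The check compares the stated windows.

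**Inputs**
- Protocol call window: 24 to 72 hours (synopsis, 5.1, 7.1, 11.2; also SAP 4).
- SAP end-of-study window: 24 to 48 hours (10.5, with 5.3).
- Time from injection to start of imaging: about 50 minutes (protocol 5.2.1). Scan length: 10 minutes (protocol 5.1).

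**Step 1. Common time origin**
- Width of protocol window: 72 − 24 = 48 hours.
- Width of SAP window: 48 − 24 = 24 hours.
- Permitted by the protocol but outside the SAP rule: 72 − 48 = 24 hours.
- Share of the permitted window: 24 / 48 = 50%.

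**Step 2. Different time origins**

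The origins are not uniform. Protocol 7.1, the synopsis Follow-up paragraph and both flow charts count from injection. Protocol 5.1, SAP 5.3 and SAP 10.5 count from the imaging session or scan. Assume the session ends about 50 + 10 = 60 minutes after injection.
- SAP rule on the injection clock: about 25 to 49 hours.
- Outside it but within the protocol's 24-72 hours: 25 − 24 = 1 hour at the start and 72 − 49 = 23 hours at the end, 24 hours in total.
- Share: again 24 / 48 = 50%.

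The choice of origin moves the edges by about an hour and does not change the result.

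**Step 3. From hours to subjects**

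Number affected = (share of subjects called after 48 hours) × (subjects injected). The documents do not give the first factor, which could lie anywhere from 0 to 1. The number therefore cannot be computed.

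**Step 4. What does not change**

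SAP 6.1.3 includes every subject with at least one injection in the safety population, and SAP 6.1.1 and 7 base the disposition table on that population. Neither depends on call timing, so adverse event counts and all denominators stay the same. Only the completion label could move.

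**Step 5. Adverse event windows**
- SAP 10.1 counts an event as treatment-emergent up to 48 hours after injection.
- Protocol 7.7.2 ends adverse event reporting at 24 hours, and the protocol's call asks only about events in those 24 hours.
- A call that meets SAP 10.5 (about 25 to 49 hours after injection) mostly comes before the SAP's 48-hour window has closed. The calls that 10.5 leaves out mostly come after it has closed.

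The call window and the two adverse event windows therefore do not fit together and need reconciling in one pass.

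**The case against.** The strongest objection is that SAP 10.5 never says that completion is derived from call timing. It defines end of study, then says separately that termination reasons are summarized. Protocol 5.5 has the reason for discontinuation noted on the case report form, which points to a recorded reason rather than one calculated from hours. SAP 5.3 defines no completion rule and qualifies its window as approximate. In practice, a subject reached at 60 hours may well be recorded as having completed.

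That limits the consequence but does not remove the contradiction. The only definition of end of study still conflicts with the SAP's own flow chart and with the protocol, and nothing says how a call at 48-72 hours is to be classified.

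A reader might infer several stronger points that the documents do not support:
- **Late-called subjects are counted as lost to follow-up.** SAP 10.5 assigns them to no category, and a subject who was reached by phone is not naturally lost.
- **Half the subjects are misclassified.** Half the window would mean half of the planned 1,800, or 0.5 × 1,800 = 900, only if calls were spread evenly over the window. No text says they were.
- **Withdrawals for adverse events are hidden because the list has no such category.** The list is introduced as non-exhaustive and ends with a residual category. SAP 10.1 summarizes events leading to discontinuation, and SAP 10.1.3 tabulates and lists serious events and lists fatal ones.

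**Conclusion.** The point holds as an inconsistency in a stated rule. SAP 5.3 and 10.5 conflict with SAP 4 and with the protocol, and on a literal reading half of the permitted call window (24 of 48 hours) falls outside the SAP's end of study. The disposition table could then understate completion. How far depends on two things the documents do not give: when calls were actually made, and whether completion is derived from the 10.5 rule or taken from a recorded reason. If it is taken from a recorded reason, the table may be unaffected. The 50% describes the window, not the subjects. No hypothesis test, adverse event count or denominator is affected. The matter should be corrected because the rule is wrong as written and cheap to repair.

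**What to change.** 1. Reconcile SAP 5.3 and 10.5 with the 24-72 hour window in SAP 4 and the protocol.
2. Use one time origin, injection or imaging session, throughout the SAP, and note that the protocol itself uses both.
3. State in SAP 10.5 that a subject whose follow-up call was made within the protocol window counts as having completed the study. Report calls outside that window as timing deviations where timing is recorded.
4. In the same edit, reconcile the call window with the 48-hour treatment-emergent window in SAP 10.1 and the 24-hour reporting window in protocol 7.7.2, so that it is clear which period the call is meant to cover.
5. Optionally, add a row for adverse event or death to the disposition table. This is a matter of layout, since those events are already summarized or listed under SAP 10.1 and 10.1.3.

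The cost is a few lines of SAP text, plus a small programming change if completion is derived rather than recorded. The completion rule and the deviation report both rely on call timing. Protocol 10.6 asks for visit dates in subject files but does not say that the date or time of the call is on the case report form, so this should be checked first.

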11. INTERIM ANALYSES

Interim analysis is not planned for this study.
